6.2 Analysis of Endpoints

Each patient will have their samples probed for evidence of lesions. During the follow-up period we will be observing if these lesions progress or regress with concurrent marker pattern changes i.e. if lesion is of low progression potential, we expect high E4 expression and low p16/MCM expression and vice versa. The final endpoint analysis will look for correlation of these biomarker patterns to the final histology or colposcopy outcome. We expect high E4 expression lesions to regress and vice versa.

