Outline the scientific justification for the research. Give an outline of the background to the study, with references to literature and other relevant research.

Give an outline of the main research questions. Give a brief outline of the intervention (if applicable) and summary of findings from previous studies (if relevant) that potentially have clinical significance.

Provide summary of the known and potential risks and benefits of any of the study procedures (where applicable)

Describe the population to be studied.

The purpose of this study is to non-invasively monitor women with histologically identified CIN2 lesions. CIN2 lesions are pre-cancer lesions that are caused by HPV. These lesions can in a small subset of patients progress onto CIN3 lesions and eventually cervical cancer. The duration of this progression is usually over 1 year (for CIN3 and longer for cervical cancer) and indeed the majority of these lesions would actually regress (especially in <30 year olds) due to immune control and HPV clearance(1–5). This understanding of CIN2 progression has led to changes in the management of CIN2 lesions, where in the past all such patients would be offered excisional treatment, we have now moved towards adopting a watch and wait policy (with usually 6 monthly colposcopy follow-ups)(6).

Our current ongoing study (17/SC/0203 - Collection of Cervical Cells at Colposcopy using a novel technique for analysis of high risk vs. low risk lesions) has demonstrated that using our non-invasive approach we can identify high-grade (CIN2+) and low-grade (CIN1/ negative) lesions using a biomarker panel. This approach has yielded numerous advantages and in particular the ability to identify lesions in their entirety together with their location on the cervix (Fig 1). This approach is now being validated on a larger cohort of patients and is being assessed to become the test of choice for HPV triage. The biomarkers we have settled on are p16/MCM (markers of CIN2+) and E4 (marker of CIN1). These markers have been independently verified by our group and others as being sensitive markers to clinically relevant disease and indeed this panel of markers, by improving the objectiveness of diagnosis, improves the sensitivity of subjective approaches such as histology/ cytology to CIN2+ lesions(7).

Fig 1. Patch stained with MCM demonstrating a CIN3 lesion in its entirety. Inset demonstrates lesion magnified

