The study will involve monitoring patients with our non-invasive technique in conjunction with colposcopy (Fig 3) to assess the feasibility of this method. The main risk to any patient is the risk of progression to CIN3 and worse cancer. However, as the majority of CIN2 patients across the UK are now offered conservative management and as many recent papers have demonstrated lesion regression in >50% of CIN2 cases this risk (over the duration of the study) is extremely low(1–6). Moreover, in order to further minimize this risk, we will follow-up these patients more intensively than the norm (usually conservative management of CIN2 involves 6-month follow-up colposcopy) with 3 monthly colposcopy visits for up to 1 year with the same named colposcopist (to reduce any inter-observer variability) where possible. If a different colposcopist is used, we will aim to mitigate

any increased variability by using and comparing colposcopic photographs taken during each colposcopy visit. This will allow us to ensure that variations in diagnosis are kept to a minimum.

Finally, as we are using biomarkers to identify lesions on the patch, any marker pattern that is suggestive of higher-grade disease will result in the patient having a colposcopic visit together with adequate counselling and biopsies/ treatment as required. We feel that this approach enables us to minimize the already low risk of progression even further thus allowing women to give informed consent in an ethical manner. There are no operceivable risks involved.

Fig 3. Study scheme demonstrating entire patient pathway including patient withdrawal points. Colposcopic photographs will be taken during each colposcopy visit and all histology will be reviewed/compared by histopathologists. A) Pathway for patients who recruited after diagnosis with CIN2, B)) Pathway for patients who recruited from the pre-existing clinical pathway either at 3 month visit (-/+ 2 week) or at the 6 month routine clinical visit (-/+ 2 week).

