4.4.2 Sample Analysis

For this feasibility study, we envisage that 10 patients will be adequate.

These will be triple stained with a pan E4 antibody to identify areas of virus infection (LSIL), along with p16/MCM to identify cells that are abnormally progressing through the cell cycle (HSIL). Images of the stained cells will be captured using a digital imaging system prior to H+E staining or staining with the Pap stain. The immunostaining and histology images will be compared against the images taken during the colposcopy examination and with the results of the biopsy analysis. For all patients, we will also request sections from the biopsy material in order to better understand how biomarker expression at the epithelial surface (in the cell-lifts) relates to expression of the same biomarkers in the underlying disease and Patch approach.

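### The pattern that 6.2 links to regression also indicates low grade at entry, so a CIN1 over-called as CIN2 would count as a correctly predicted regression

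*Protocol*

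**What the plan says.** Section 6.2 gives the expected pattern, "if lesion is of low progression potential, we expect high E4 expression and low p16/MCM expression and vice versa", and introduces it as something observed alongside changes over follow-up. It then plans to correlate the patterns with the final histology or colposcopy outcome, and expects lesions with high E4 to regress.

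The same markers are given a meaning for present grade in two other places:

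- Background and Rationale: "The biomarkers we have settled on are p16/MCM (markers of CIN2+) and E4 (marker of CIN1"). The panel is presented there as separating CIN2+ from CIN1 or negative.
- Section 4.4.2: the low-grade stain is described as "pan E4 antibody to identify areas of virus infection (LSIL"). The same sentence assigns p16/MCM to HSIL.

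Entry (4.3.1, 4.3.2) rests on a histological diagnosis of CIN2. The Background says of the panel that it "improves the sensitivity of subjective approaches such as histology/ cytology to CIN2+ lesions".

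Two planned items bear on the entry grade. The Fig 3 caption says "all histology will be reviewed/compared by histopathologists". Section 4.4.2 says "For all patients, we will also request sections from the biopsy material", with the aim of relating marker expression at the surface to that in the underlying tissue. Section 6.2 mentions neither.

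**The concern.** One marker reading does two jobs. In the Background and 4.4.2 it points to a low-grade lesion now; in 6.2 it points to regression later. A woman whose first patch is E4-high and p16/MCM-low could have a CIN2 of low potential, a CIN2 that the patch did not pick up, or a CIN1 that was over-called on biopsy. If she joined at 3 or 6 months, she could also have a CIN2 that had already begun to regress.

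For the over-called CIN1, a low-grade result at the end is simply the correct grade. Section 6.2 as written would count it as regression and as agreement with the expected pattern. The Ethics section says that CIN1 has a very low risk of progression, so such women would fall almost wholly on the expected side.

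The primary objective is to find patterns that go with the course of CIN2 lesions. At stake is whether the study would report such a pattern when, in part, it had re-graded the entry biopsies.

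**Working it through.** The protocol has no figure to reproduce here: the sample size of 10 comes without a formula, effect size or precision target. The check asks what 6.2 would show if the markers had no prognostic value in true CIN2.

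**Inputs from the protocol (Background)**
- Patch sensitivity for CIN2+ 88%, positive predictive value 84%, pilot of 50 patients.
- Regression in more than 50% of CIN2; r = 0.50 is used.

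**Assumptions not in the protocol**
- Share f of entry CIN2 that is really CIN1: 10%, 20% or 30%.
- CIN2+ prevalence p in the pilot: 40%, 50% or 60%.
- Every over-called CIN1 ends as regressed.
- A true CIN2 shows the pattern with probability 1 − 0.88 = 0.12, whatever its course; a CIN1 shows it with probability equal to the patch specificity.

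**Step 1: implied specificity**

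False-positive rate = 0.88 × p × (0.16/0.84) / (1 − p).

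At p = 0.5 this is 0.88 × 0.1905 = 0.168, so specificity is 0.832. At p = 0.4 and 0.6 it is 0.888 and 0.749.

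**Step 2: apparent regression**

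- With the pattern: [f × spec + (1 − f) × 0.12 × r] / [f × spec + (1 − f) × 0.12]
- Without it: [f × (1 − spec) + (1 − f) × 0.88 × r] / [f × (1 − spec) + (1 − f) × 0.88]

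At f = 0.10 and specificity 0.832:

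- With: (0.0832 + 0.054) / (0.0832 + 0.108) = 0.137 / 0.191 = 0.72
- Without: (0.0168 + 0.396) / (0.0168 + 0.792) = 0.413 / 0.809 = 0.51

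| Over-call f | With pattern | Without | Expected women with pattern, of 10 |
|---|---|---|---|
| 10% | 72% | 51% | 1.9 |
| 20% | 82% | 52% | 2.6 |
| 30% | 87% | 54% | 3.3 |

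Over the three prevalences and three over-call rates the gap runs from 19 to 35 percentage points. With f = 0 it is zero.

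**Step 3: a second set of assumptions, not tied to the pilot figures**

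Let an over-called CIN1 show the pattern, and be read as regressed, each with probability 0.95. Let a true CIN2 show the pattern with probability 0.10 or 0.30, and regress with probability 0.50 or 0.60, independently. The apparent odds ratio for regression is then 1.0 with no over-calling, 1.5 to 2.7 at 10% and 2.0 to 4.4 at 20%. The direction is the same.

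**Step 4: what 10 women can show**

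- Chance of at least one over-called CIN1: 1 − 0.9^10 = 65% at a 10% rate; 1 − 0.8^10 = 89% at 20%.
- Under Step 3, a two-sided Fisher test at n = 10 would give p < 0.05 in only 0.4% to 8% of studies for over-call rates of 10% to 40%.

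**The case against.** **The size is largely assumed.** This stands. The 88% and 84% refer to CIN2+, which includes CIN3, in a population that the protocol calls enriched. They do not describe the E4-high, p16/MCM-low pattern: a missed patch need not be E4-high, and the panel's low-grade class includes negative women. If the pilot was judged against histology, its 12% of misses already contain over-calls. At f = 0.10, over-calls alone would give 0.10 × 0.832 = 0.083, which fits within 0.12. At f = 0.20 they would give 0.166, which does not, unless over-calling is concentrated in CIN2. On that reading the pattern would also rest on about 0.12 × 10 = 1.2 women. The 20% and 30% rows are therefore weak.

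**Section 6.2 describes serial patches, not one entry reading.** This stands in part. An over-called CIN1 would tend to stay E4-high throughout, while a regressing CIN2 would change. But 6.2 does not confine the final correlation to change, and its last expectation concerns high-E4 lesions as such.

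**Safeguards are planned, and details may sit elsewhere.** Fig 3 is not visible in the text reviewed and an SAP may exist. A reader might infer that the review and the sections have no role at all in confirming entry; that cannot be asserted. What can be said is that 6.2, which fixes the pattern, the outcome and the expected direction, gives them none.

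**It is a pilot.** Section 4.2 claims only initial utility, and no test is specified. A reader might infer that the study would wrongly prove the pattern predictive; Step 4 does not support that. A reader might also infer that the protocol defines the pattern as CIN1; it calls E4 a marker of CIN1 and does not define the combined reading. Finally, a pattern that flags over-called CIN1 could still help triage women labelled CIN2, but it would not show that CIN2 lesions regress.

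**Conclusion.** The concern holds as a bias in the correlation that 6.2 states. Over-calling at entry pushes the result in the expected direction whenever it occurs, provided that over-called CIN1 tends to show the marker reading that the protocol itself ties to CIN1, and tends to end low-grade.

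The size cannot be fixed from the protocol. The most defensible illustration is the 10% row: a gap of about 21 points, on about 2 of 10 women, with the over-call rate and the pilot prevalence both assumed. In a study this small, with no threshold set for agreement, the consequence is a misleading descriptive conclusion. It is worth correcting in the protocol because the material needed is already planned.

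**What to change.** Amend 6.2 as follows:

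- The entry grade used in the analysis is the one from the histopathologists' review (Fig 3 caption), recorded without reference to the patch result.
- The correlation of pattern with outcome is shown for all women, and again for women whose entry grade is CIN2 on review.
- Women whose entry biopsy is not CIN2 on review are listed separately and not counted as regressed CIN2. They stay in the feasibility results.
- The final outcome remains histology or colposcopy as planned, with the source stated for each woman.
- The stained entry-biopsy section (4.4.2) is shown beside the first patch, with the time between them, as description only.

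The last item should not be used to reclassify grade. Calling tissue with low p16/MCM a low-grade lesion would erase CIN2 of low potential. In women who join at 3 or 6 months, tissue that is high with a patch that is low may be real regression and not a patch miss.

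The cost is an amendment to 6.2 and an instruction to record the reviewed grade without reference to the patch result. The CIN2-on-review analysis may rest on slightly fewer than 10 women, which is why both analyses are shown. Eligibility and patient care do not change.

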6. ETHICS

The main ethical consideration is the intensive follow-up for these patients over the course of one year i.e. up to 4 visits vs. 2. However, we feel this is justified as this work could enable us to better understand marker patterns that correlate with regression/ progression and will also enable us to assess the feasibility of non-invasively sampling these patients which may lead to a better patient

experience in the future. A further consideration is that of only focusing of the CIN2 patients rather than the CIN1 patients. This stems from the current understanding that CIN1 patients would have a very low risk of progression and indeed do not require treatment and thus this patient group is no exposed to the consequences of excisional treatment. In contrast the CIN2 patients would be offered treatment or conservative management and therefore this work has the potential to better inform us on which patients to offer conservative or excisional treatment.

7.1 Participant Confidentiality

The study staff will ensure that the participants' anonymity is maintained. The participants will be identified only by a participant's ID number on the CRF and any password protected electronic database that will be stored on secure NHS computers. All documents will be stored securely and only accessible by study staff and authorised personnel. The study will comply with the Data Protection Act, which requires data to be anonymised as soon as it is practical to do so.

7.2 Other Ethical Considerations

Only participants able to understand the study will be involved

7. DATA HANDLING AND RECORD KEEPING

All study data will be entered on a password protected MS Excel spreadsheet by the research nurse. This database will only be accessible by those directly involved in this study. The participants will be identified by a study specific participants number and/or code in any database. The name and any other identifying detail will NOT be included in any study data electronic file.

